2.3.2 Bleed-Related Objectives and Endpoints

The bleed efficacy objectives for this study are as follows:

- To evaluate the clinical effect of prophylactic emicizumab on the number of bleeds over time
- To evaluate the reduction in bleeding rate on-treatment with emicizumab compared with the patient's historical bleeding rate (intra-patient comparison, only patients in Cohort A who previously participated in the non-interventional study (NIS), as patients enrolled in Cohorts B and C will not have previously participated in the NIS)
- To characterize the efficacy of up-titration on an intra-patient level, based on the number of bleeds over time.

The endpoint is the bleed rate and is defined as the number of bleeds over the efficacy period. Different analyses will be conducted as outlined in the sections below.

2.3.2.1 Treated Bleeds

A bleed is considered to be a “treated bleed” if it is directly followed (i.e., there is not an intervening bleed) by a hemophilia medication reported to be a “treatment for bleed”, irrespective of the time between the treatment and the preceding bleed. A bleed and the first treatment thereafter are considered to be pairs (i.e., one treatment belongs to one

bleed only), with the following exception: If multiple bleeds occur on the same calendar day, the subsequent treatment is considered to apply for each of these multiple bleeds.

Bleeds due to surgery/procedure are not included in the analysis. Only treatments that were recorded as “treatment for bleed” are included in the determination of a treated bleed. Note that a bleed can be treated with more than one treatment.

72-Hour Rule:

Two bleeds of the same type (e.g., “joint”, “muscle”, or “other”) and at the same anatomical location are considered to be one bleed if the second bleed occurs within 72 hours from the last treatment for the first bleed. The last treatment is defined as the last treatment before a new bleed occurs, either in the same or in a different location. This is consistent with the above definition that bleeds and treatments are considered to be pairs.

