practice and ideally during a period when the bleeding status of the child is well controlled and stable. Vaccinations should not be administered on the same day as an emicizumab administration but ideally at a timepoint between two emicizumab administrations (>48 hours after emicizumab administration). Children who receive vaccinations must be carefully followed for any adverse reactions in the subsequent days following vaccine administration.

- Caution should be taken if anti-fibrinolytics are used in conjunction with rFVIIa in patients receiving emicizumab

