4.7.8 Bleed Definitions

Definition of a Bleed

For the purposes of the efficacy analyses, a standardized definition of bleed, adapted from standard criteria defined by the Subcommittee on Standards and Criteria, FVIII/FIX

subcommittee of the ISTH and similar to that used in a recent clinical study, will be utilized in this study (Blanchette et al. 2014; Mahlangu et al. 2014).

- An event is considered a bleed if coagulation factors are administered to treat signs or symptoms of bleeding (pain, swelling, etc.). An additional definition of all bleeds (i.e., both treated and not treated with coagulation factors) will be applied as well.
- Bleeds starting from the first sign of bleed and ending 72 hours after the last treatment for the bleed, within which any symptoms of bleeding at the same location or injections are \leq 72 hours apart, are considered the same bleed.
- Any injection to treat the bleed, taken $>$ 72 hours after the preceding injection, is considered the first injection to treat a new bleed at the same location.
- Any bleed at a different location is considered a separate bleed regardless of time from last injection.

Definitions of Bleed Sites

- Target joints are defined as a major joint (e.g., hip, elbow, wrist, shoulder, knee, and ankle) into which repeated bleeds occur (frequency of \geq 3 bleeds into the same joint over the last 24 weeks prior to study entry)
- Joint bleeds (sites as per the Bleed/Medication Questionnaire)
- Muscle bleeds (sites as per the Bleed/Medication Questionnaire)
- Other bleeds (sites as per the Bleed/Medication Questionnaire)

Definitions of Bleed Types

In addition, the assessment of a bleed will be separated into spontaneous bleeds, traumatic bleeds and bleeds related to procedure/surgery. Both spontaneous bleeds (i.e., the occurrence of hemorrhage where neither the patient nor a caregiver can identify a reason) and traumatic bleeds (i.e., hemorrhage occurring secondary to an event such as trauma, “strenuous” activity, or “overuse”) will be collected.

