- ^d A complete physical examination will be performed at screening and targeted physical examination will be performed at subsequent visits. Targeted physical examination of joints (for bleeds, evidence of arthropathy) and skin (for bruises, hematomas, and injection-site reactions), in addition to other organ systems as clinically indicated and/or report of new or worsening adverse event.
- ^e Body temperature (oral, rectal, axillary, or tympanic), blood pressure, pulse rate, respiratory rate, height/length, and weight to be entered into eCRF. If Screening and Week 1 occur on the same date, the vital signs should be measured only once. If Screening and Week 1 occur on different dates, vital signs should be repeated for both assessments.
- ^f Concomitant medications (e.g., extra pain medication with bleed) will be asked about at each clinic visit and documented in the eCRF, excluding treatments for bleeds (i.e., bypassing agents and other medications to treat bleeds), which will be collected on the bleed/medication questionnaire. Hemostatic medications to treat or prevent bleeds in the 4 weeks prior to starting emicizumab will be collected on eCRF.
- ^g If screening ECG abnormal, repeat at Week 1 (or Week 2 if Screening and Week 1 occur on the same date). ECGs will also be performed 4 weeks after starting emicizumab or after each dose up-titration, as well as at study completion/early termination.
- ^h In case of up-titration, additional assessments including PK, PD biomarkers, anti-emicizumab antibodies, safety laboratory samples, and ECG will be required, with the schedule of assessments resetting back to Week 1, including an ECG.

Appendix 1

Schedule of Assessments (cont.)

- ⁱ Laboratory data (performed locally) includes complete blood count with differential and serum chemistries (i.e., sodium, potassium, chloride, glucose, blood urea nitrogen, creatinine, calcium, phosphorus, magnesium, creatine phosphokinase, total protein, albumin, creatinine, total and direct bilirubin, alkaline phosphatase, ALT, and AST). Female patients of childbearing potential will be required to have a negative serum pregnancy test result at screening and urine pregnancy tests performed at Weeks 13, 25, 37, and 49; every 12 weeks starting from Week 57; and study completion/early termination.

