2.3.2.2 All Bleeds

Given that some patients may report bleeds that they did not treat, ‘all bleeds’ will be analyzed as an additional endpoint definition to treated bleeds and comprise both treated and non-treated bleeds. In this definition, all bleeds are included, irrespective of treatment with coagulation factors, with the following exception: Bleeds due to surgery/procedure are excluded as for the ‘treated bleed’ analysis.

The endpoint of all bleeds fulfills the adapted ISTH criteria, as described in the protocol and the 72-hour rule, in particular. For treated bleeds, it is implemented exactly as defined for the ‘treated bleed’ definition (see Section [2.3.2.1](#)). For non-treated bleeds (not followed by any treatments with coagulation factors before the recording of a subsequent bleed), it is implemented by calculating a treatment-free period of 72 hours from the bleed itself.

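### SAP 2.3.2.1 puts no drug-class limit on what makes a bleed treated, so a bleed managed only with a non-factor drug can be counted as treated, contrary to Protocol 4.7.8 and SAP 2.3.2.2

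*SAP*

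**What the plan says.** SAP 2.3.2.1 makes a bleed treated when it "is directly followed (i.e., there is not an intervening bleed) by a hemophilia medication reported to be a" treatment for bleed, however long after the bleed that treatment comes. It then adds that only entries with that recorded reason "are included in the determination of a treated bleed". The test is therefore the recorded reason; the class of drug is not part of it.

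Protocol 4.7.8 uses a different test: "An event is considered a bleed if coagulation factors are administered to treat signs or symptoms of bleeding". Its additional all-bleeds definition separates treated from untreated events by whether coagulation factor was given.

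SAP 2.3.2.2 takes treated bleeds over unchanged from 2.3.2.1, but describes non-treated bleeds as those "not followed by any treatments with coagulation factors before the recording of a subsequent bleed". SAP 4.4.1.1 presents the 2.3.2.1 rule as the adapted ISTH definition and points to Protocol 4.7.8. No departure from the protocol is declared.

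On what reaches the questionnaire, Protocol 4.6 sends medications given to treat a bleed to the handheld device only. Footnote f of the Schedule of Assessments (Protocol Appendix 1, repeated in SAP Appendix 2) describes these as "bypassing agents and other medications to treat bleeds".

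**The concern.** The SAP applies two criteria to one split. A bleed whose only recorded treatment is a non-factor drug meets the 2.3.2.1 rule for treated and also the 2.3.2.2 rule for non-treated. Under Protocol 4.7.8 it is not a treated bleed.

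The 2.3.2.1 rule carries into treated spontaneous bleeds (2.3.2.3), treated joint bleeds (2.3.2.4) and treated target joint bleeds (2.3.2.5). It also carries into the treated-bleed versions of the intra-patient comparison (2.3.2.6) and the up-titration analysis (2.3.2.7). The study tests no hypothesis, so these rates are themselves the efficacy result, and what counts as an event matters correspondingly. Two programmers working from the same SAP could report different counts.

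**Working it through.** There is no plan figure to reproduce: the sample size is feasibility-based and no test is planned. The check is a comparison of definitions, followed by a scale calculation.

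**1. One bleed under three rules.** Take a bleed followed only by a non-factor drug whose recorded reason is treatment for bleed.

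| Place | Criterion | Result |
|---|---|---|
| SAP 2.3.2.1 | hemophilia medication with that recorded reason | treated |
| Protocol 4.7.8 | coagulation factor given | not treated; counts under all bleeds only |
| SAP 2.3.2.2 | no coagulation factor before the next recorded bleed | non-treated |

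**2. Can such an entry occur?** Footnote f expects medications besides bypassing agents on the questionnaire. Protocol 3.1 counts emicizumab as a hemophilia medication, so that term is wider than coagulation factor. Against this, the last paragraph of Protocol 4.7.8 equates hemophilia medication given for a bleed with bypassing agents. The list of selectable products is not in the documents. The entry is plausible but not established.

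**3. The 72-hour window.** SAP 2.3.2.1 runs it from the last treatment; SAP 2.3.2.2 runs it from the bleed itself when the bleed is non-treated. Suppose a bleed at hour 0, a non-factor dose at hour 24, and a second bleed of the same type and site at hour 80.
- Under 2.3.2.1: 80 − 24 = 56 hours, within 72, so one bleed.
- Under 2.3.2.2: 80 − 0 = 80 hours, beyond 72, so two bleeds.

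The all-bleeds count can therefore change too, but only through merging.

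**4. Scale.** Both documents define ABR as bleeds divided by days in the efficacy period, times 365.25. One additional treated bleed adds 365.25/d to an individual ABR, and 365.25/(d × n) to the mean over n patients with the same follow-up.

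| Days d | Individual ABR | Mean, n = 10 | Mean, n = 60 |
|---|---|---|---|
| 84 (12 weeks) | 4.35 | 0.43 | 0.072 |
| 182 (26 weeks) | 2.01 | 0.20 | 0.033 |
| 364 (52 weeks) | 1.00 | 0.10 | 0.017 |

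The 182-day row with n = 10 approximates Cohorts B and C at the primary analysis (about 10 patients each, efficacy period of about 6 months, Protocol 3.1). The 364-day row with n = 60 approximates Cohort A. These are effects per misclassified bleed. The documents give no frequency, so a total cannot be computed.

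**5. Direction.** Counting these bleeds as treated raises the treated-bleed rate. The intra-patient ratio divides the on-study rate by the historical rate. If such bleeds form a larger share of counted bleeds on study, the ratio rises; if a larger share in the NIS, it falls; if equal shares, it is unchanged.

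**The case against.** The best reply is that no difference was intended. Protocol 4.7.8, which SAP 4.4.1.1 cites, glosses treatment of a bleed as a bypassing agent, and bypassing agents are coagulation factors. SAP 2.3.2.2 uses its two phrases as complements, as if they meant the same. The other medications in footnote f could simply be FVIII, and footnote m describes the questionnaire as recording injections. On that reading the issue is one of terminology.

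This stands as evidence of intent and is why confidence is only moderate. It does not settle the matter. The gloss is absent from SAP 2.3.2.1, which is the text to be programmed. In the same sentence the protocol glosses prophylaxis as weekly emicizumab, which does not fit Cohorts B and C, so it is a loose description rather than a working definition. Footnote f is wider on its face.

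Three stronger readings are tempting but unsupported:
- That any hemophilia medication after a bleed makes it treated. It does not: the entry must be recorded as treatment for bleed, so a routine emicizumab dose does not qualify.
- That anti-fibrinolytics given alone are a documented route. Protocol 4.6.1 says only "Caution should be taken if anti-fibrinolytics are used in conjunction with rFVIIa in patients receiving emicizumab"; factor is given there, so the bleed is treated under every definition. Protocol 4.6.2 bars the combination with aPCC or Byclot. Use alone is not prohibited, but neither section describes it.
- That the wording favors emicizumab. Counting extra treated bleeds raises the on-study rate.

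**Conclusion.** The inconsistency is real and lies in the text. SAP 2.3.2.1 admits any hemophilia medication recorded as treatment for bleed, whereas Protocol 4.7.8 and SAP 2.3.2.2 divide bleeds by coagulation factor. Bleeds managed only with a non-factor drug can be counted as treated. A reader might infer that they will be; the documents do not show that, because the questionnaire's drug list is not available and Protocol 4.7.8 points to a narrower intent.

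The effect per bleed is noticeable in Cohorts B and C (0.20 on a 10-patient mean at 182 days) and small in Cohort A (0.017 on a 60-patient mean at 364 days). Those figures assume equal follow-up within a cohort and one misclassified bleed. The point merits correction because the inconsistency reaches every treated-bleed endpoint and is easily removed. Confidence is moderate.

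**What to change.** In SAP 2.3.2.1, state that only coagulation factor products (bypassing agents or FVIII) recorded as treatment for bleed make a bleed treated and start the treatment-based 72-hour window. Attach the list of qualifying products. Count bleeds followed only by non-factor medication as non-treated within all bleeds, with the window running from the bleed as in 2.3.2.2. Apply the same filter on the recorded agent to the NIS period, so that both sides of the intra-patient ratio use one definition.

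If the broader rule is in fact wanted, declare it as a departure from Protocol 4.7.8, justify it, and align 2.3.2.2.

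The cost is one phrase, a product list and one programming filter. Protocol 3.1 already has the agent recorded on the device, so no new study data are needed. For the NIS this assumes the agent was captured in the same way, as SAP 2.3.2.6 implies when it refers to equal granularity in both periods.

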- Spontaneous bleeds: Bleeds will be classified as spontaneous if a caregiver records a bleed when there is no known contributing factor such as definite trauma, antecedent “strenuous” activity or “overuse” or “procedure/surgery.” The determination of what constitutes “strenuous” or “overuse” will be at the discretion of the caregiver. For example, light jogging may be considered “non-strenuous” while sprinting may be considered “strenuous,” lifting of weights for a short period of time may be considered “moderate use” while repetitive weightlifting may be considered “overuse.”
- Traumatic bleeds: Bleeds should be classified as traumatic if a caregiver records a bleed when there is a known or believed reason for the bleed. For example, if a patient were to exercise “strenuously” and then have a bleed in the absence of any obvious injury, the bleed would be recorded as a traumatic bleed because, although no injury occurred, there was antecedent “strenuous” activity. Bleeds with preceding injuries would certainly be classified as traumatic.
- Bleeds related to procedure/surgery: such as hematomas resulting from any surgeries or invasive procedures (e.g., tooth extractions, venipuncture, or SC drug

administrations) or invasive diagnostic procedures (e.g., lumbar puncture, arterial blood gas determination, or any endoscopy with biopsy, etc.) would not be counted as bleeds but will be collected on the bleed/medication questionnaire. Bleeds related to procedure/surgery are not associated with any trauma except procedure/surgery-induced trauma.

Caregivers will complete the bleed/medication questionnaire any time a patient experiences a bleed. At this time, the caregivers will also answer questions detailing the location, type and time of the bleed. Caregivers will also complete this medication questionnaire weekly as well as any time a hemophilia medication is administered, whether for prophylaxis (i.e., weekly emicizumab) or for treatment of bleed (i.e., bypassing agent).

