4.4.1 Efficacy Endpoint

4.4.1.1 Bleed Rate

A bleed is defined in two ways. The first definition uses adapted ISTH definition of a bleed ([Blanchette 2014](#); see Section [2.3.2.1](#); see Protocol Section 4.7.8). The second definition is counting all the bleeds regardless of the treatment (see Section [2.3.2.2](#)).

The number of bleeds over time (bleed rate) will be calculated using a negative binomial (NB) regression model, which accounts for different follow-up times, with time that each patient stays in the study (efficacy period) included as an offset in the model. In addition, the number of bleeds will also be annualized for each patient using the following formula:

$$ABR = (Number\ of\ bleeds/number\ of\ days\ during\ the\ efficacy\ period) \times 365.25.$$

For the interim CSRs, the population ABR may not be robust as it might be driven by only a few extreme observations because of the short follow up time. Therefore, the bleed rate will be characterized through individual patient data collected on the BMQ. In addition, with such short follow up, the NB model might not converge or the results might be unreliable. For all the patients, the number of bleeds will be described with use of descriptive statistics. The individual ABR will be calculated for patients who have been on the study for at least 12 weeks on the same dose (including the loading doses) with use of the given formula above.

The number of bleeds, types, and locations of bleed will be summarized for all patients and listed for each patient individually. Several exploratory analyses will be conducted to characterize the type, location, frequency, and pattern of bleeds.

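### The SAP's 72-hour rule omits the protocol's provision that an injection given more than 72 hours after the preceding one starts a new bleed, but is presented as the protocol's definition

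*SAP*

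**What the plan says.** Protocol 4.7.8 sets the bleed definition for the efficacy analyses, and Protocol 6.4.1 refers back to it. A bleed runs from its first sign to 72 hours after its last treatment. An injection to treat the bleed that comes more than 72 hours after the preceding injection "is considered the first injection to treat a new bleed at the same location". This provision depends on the time between injections, not on whether the caregiver made a new bleed entry.

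SAP 2.3.2.1 pairs a bleed entry with the treatment that directly follows it, "irrespective of the time between the treatment and the preceding bleed", and adds: "Note that a bleed can be treated with more than one treatment". Its 72-hour rule concerns two recorded bleeds of the same type and location, which "are considered to be one bleed if the second bleed occurs within 72 hours from the last treatment for the first bleed". Under this rule, whichever treatment precedes the next recorded bleed is the last one, however late it was given.

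SAP 2.3.2.2 reuses this rule for the treated part of all bleeds. For non-treated bleeds it again works from entries ("before the recording of a subsequent bleed"). It then states: "The endpoint of all bleeds fulfills the adapted ISTH criteria, as described in the protocol and the 72-hour rule, in particular". SAP 4.4.1.1 says "The first definition uses adapted ISTH definition of a bleed" and cites both SAP 2.3.2.1 and Protocol 4.7.8.

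**The concern.** The SAP can merge recorded entries or leave them separate. It cannot create a bleed from a long gap between injections, as the protocol requires. This has three consequences:

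- A late injection with no new entry stays with the old bleed and is not counted.
- That injection becomes the last treatment, so the merging window restarts from it and can absorb a later, properly recorded entry at the same site.
- Even with a complete diary, a re-bleed entered inside the 72 hours but injected after them is merged by the SAP and split by the protocol.

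The bleed rate is the efficacy endpoint, so the counting rule determines the result. The treated spontaneous, joint and target-joint endpoints and the treated part of all bleeds are built on the same count. Because the SAP claims conformity, a reader of the results would not know that the counts follow a different rule.

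**Working it through.** The plan states no figure to reproduce: the study is descriptive and its sample size has no statistical basis. The check applies both rules to constructed sequences at one site and converts the difference to ABR.

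**Rules applied**

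- Protocol 4.7.8: a gap between injections above 72 h starts a new bleed.
- SAP 2.3.2.1: a second same-site entry no more than 72 h after the last treatment is merged; otherwise it counts separately.

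**Sequences (knee)**

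| Sequence | Protocol | SAP | SAP plus the rule |
|---|---|---|---|
| (a) One entry; injections days 0, 1 and 8 | 2 | 1 | 2 |
| (a) with a day-8 entry recovered | 2 | 2 | 2 |
| (b) Entry and injection day 0; injection only day 8; entry and injection day 10 | 2 | 1 | 2 |
| (b) without the day-8 injection | 2 | 2 | 2 |
| (c) Entry hour 0, injection hour 1, entry hour 70, injection hour 76 | 2 | 1 | 2 |
| (c) with the second injection at hour 71 | 1 | 1 | 1 |
| Control: second entry at hour 100 | 2 | 2 | 2 |

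- In (a) the long gap is 8 − 1 = 7 days = 168 h. The protocol splits; the SAP has only one entry to count.
- In (b) the day-8 injection is 192 h after the first, so the protocol splits there. Under the SAP it is the last treatment before the day-10 entry, which follows by 48 h and is merged. Removing that injection raises the SAP count from 1 to 2.
- In (c) the second entry is 70 − 1 = 69 h after the last treatment, so the SAP merges. The injections are 76 − 1 = 75 h apart, so the protocol splits.

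Further patterns with a single entry at hour 0: injections at 0, 24 and 96 h (longest gap exactly 72 h) give 1 under both rules; injections at 0, 80, 160 and 240 h give protocol 4, SAP 1.

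**Direction.** The missing rule only splits. In 200,000 random one- and two-site sequences, with the SAP's pairing and its cut-off for the last treatment kept, adding the rule lowered the count in none.

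**Size of one lost bleed.** ABR = bleeds ÷ days × 365.25 (Protocol 6.4.1, SAP 4.4.1.1). Cohort sizes are about 60, 10 and 10. Follow-up is taken as 52 weeks (364 days) in Cohort A and, from the approximate 6 months in Protocol 3.1, 26 weeks (182 days) in Cohorts B and C.

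- One patient: 365.25/364 = 1.003; 365.25/182 = 2.007.
- Pooled, Cohort A: 365.25/(60 × 364) = 0.0167.
- Pooled, Cohort B or C: 365.25/(10 × 182) = 0.201.

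**Assumed frequency.** None is given, so suppose 0%, 10% or 20% of patients lose one bleed each.

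- Cohort A (0, 6 or 12 patients): pooled ABR too low by 0, 6 × 0.0167 = 0.10, or 12 × 0.0167 = 0.20.
- Cohort B or C (0, 1 or 2 patients): too low by 0, 0.20, or 2 × 0.201 = 0.40.

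**The case against.** **Missing entries should be rare.** Protocol 4.7.8 has the caregiver complete the questionnaire at every bleed and "any time a hemophilia medication is administered". SAP 2.2 adds weekly prompts, joint review at clinic visits, sponsor checks and data clarification requests. These may recover some entries, and in (a) a recovered entry removes the difference. They do not supply the rule, which needs no new entry to apply.

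**Case (c) can be read as one bleed.** The protocol also treats same-site symptoms no more than 72 h apart as one bleed, and the hour-70 entry falls inside that window. But the protocol closes the first bleed at 1 + 72 = 73 h, and its late-injection provision covers any injection beyond the limit, including the one at hour 76. The window in (c) is narrow, and (a) and (b) carry the point without it.

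**The remedy creates bleeds without an entry.** The listed injection fields carry no site, so the new bleed takes an assumed location and cause, and an injection for an unrecorded bleed elsewhere could be credited to the earlier site. This stands as a limitation: with several sites, the SAP plus the rule is not guaranteed to equal the protocol count. Same-location attribution is nevertheless the protocol's own wording.

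**The size is assumed.** This stands. Protocol 3.3.1 reports or predicts a median ABR of 0 at effective exposure. If that held here, at least half of patients would have no bleeds, and 20% of all patients would be at least 0.20/0.50 = 40% of those who bleed. The upper end of the range may be high.

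**No formal decision depends on the count.** True, as there is no hypothesis test. The bleed rate is still the result that will be reported and read.

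**Conclusion.** The point holds. Followed as written, the SAP yields treated-bleed counts that are not the protocol's, while stating that they are. The two rules agree when all injections for a bleed are no more than 72 h apart, and when a late re-bleed has its own entry more than 72 h after the last treatment. Where the omission matters it lowers the count, on the condition that the rest of the SAP algorithm stays as it is.

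The effect per lost bleed follows from the ABR formula. The total effect is unknown because no frequency is given, and the 0–20% range is only an illustration. In the intra-patient comparison either the non-interventional or the on-study period can be lowered, so the direction of the effect on the rate ratio is not known. This is a mismatch in the endpoint definition that should be fixed, not a demonstrated large bias.

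**What to change.** Add to SAP 2.3.2.1 a sentence to this effect: *A treatment for bleed given more than 72 hours after the preceding treatment for that bleed starts a new treated bleed at the same location (Protocol 4.7.8).* In addition:

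- State which cause such a bleed takes in the treated spontaneous analysis (SAP 2.3.2.3) when it has no entry of its own, for example that of the preceding entry.
- Apply the sentence to the non-interventional and on-study periods alike, since SAP 2.3.2.6 already intends the detailed definition for both.
- Keep the current algorithm as a sensitivity analysis.
- Keep the cut-off of the last treatment at a bleed in a different location, but describe it as an attribution convention, needed because injections carry no site. Note that it can split one continuing bleed when an injection treats two sites.

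Alternatively, declare the departure from Protocol 4.7.8 and report a count under the protocol rule beside the SAP count, with the same limitation on site.

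The cost is SAP wording and one derivation program. No new data are needed: Protocol Appendix 1 (footnote m) already collects the date and time of each injection. Reported treated-bleed rates could rise but not fall.
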